### 8.3.3 Other safety parameters

Echocardiograms will be performed at regular intervals and according to a standard protocol.

The centrally read echocardiogram results will be used for analysis.

The maximum decline in mean ejection fraction (EF) from baseline will be summarized in a table by cohort with the following cutoffs: decline of  $>10\%$ , decline of  $>5\text{-}\leq 10\%$  and decline of  $>0\text{-}\leq 5\%$ . Moreover, the number of subjects with any mean EF that declines by  $>10\%$ ,  $>5\text{-}\leq 10\%$  or  $>0\text{-}\leq 5\%$  will be summarized by measurement time and cohort.

A listing of all mean EFs by time point for subjects with any mean EF that declines by  $>10\%$  or  $>5\text{-}\leq 10\%$  will be provided.

Moreover, for the following parameters: diastolic volume, left ventricular ejection fraction (LVEF) single plane, LV fractional shortening, LVPW diastolic thickness, systolic volume and ventricular septum diastolic thickness, the following analyses will be performed:

Raw data and changes from baseline (Screening) as well as percent changes from baseline will be described by measurement time, for each cohort.

Graphs of individual subject values (spaghetti plots) will be generated for each parameter and each cohort.

A summary table with the number and percentage of subjects with abnormally low, normal, and abnormally high values will be generated by measurement time, for each cohort.

Overall interpretation of echocardiograms will be listed by time point by cohort.

Graphs of actual mean(SE), mean of change from baseline(SE) by cohort over time will be plotted for mean ejection fraction.

Weight and BMI will be measured (see section [12.1](#)) for each cohort at the screening visit and at the completion visits.

Raw data and changes from baseline (Day 1) will be described by measurement time, for each cohort and listed.

Complete physical examination will be measured (see section [12.1](#)) for each cohort at the screening visit, on Day 1, Week 1 and then once a week after.

Results from physical examination will be described by measurement time, for each cohort.

All physical examinations over time for any subject with any clinically significantly abnormal physical examinations will be listed as well as all individual data.

Pregnancy test will be performed (see section [12.1](#)) for each cohort at the screening visit and at the completion visits.

Positive pregnancy test will be listed as well as all individual data.

Toxicology testing will be listed.

## 9. Efficacy data

All efficacy analyses will be performed on the Safety set and, if necessary only, on the Per Protocol set.

### 9.1 Analysis Specifications

#### 9.1.1 Level of Significance

No significance testing will be performed. However, a two-sided Clopper-Pearson 95% CI will be constructed around the proportion of subjects with SVRx and other virologic response parameters, for each cohort.

#### 9.1.2 Data Handling Rules

Plasma HCV RNA values will be determined using the Roche Cobas Ampliprep/Cobas Taqman v2.0 assay with a lower limit of quantification (LLOQ) of 15 IU/mL and a limit of detection (LOD) of 15 IU/mL.

For the purpose of the analysis HCV RNA results “HCV RNA <15 IU/mL” will be imputed by LLOQ-1 IU/mL = 14 IU/mL before log transformation and “HCV RNA not detected” will be imputed by LOD-2 IU/mL= 13 IU/mL before log transformation.

### 9.2 Primary Efficacy Endpoint

The primary efficacy endpoint is sustained virologic response 12 weeks after the actual end of treatment (SVR12).

#### 9.2.1 Definition

SVR12 is classified as success or failure according to the following algorithm based on HCV RNA values 12 weeks after the actual end of treatment.

**SVR12 is classified as a success (1) if** at the time point of SVR12, HCV RNA value(s) meet one of the following:

- HCV RNA Not detected or
- < LLOQ detected and
  - the sample is a confirmation\* visit or
  - the sample is the last available HCV RNA measurement or
  - at the next available measurement, HCV RNA not detected or HCV RNA < LLOQ detected
- ≥ LLOQ and
  - the sample is not from a confirmatory visit\* and
  - not the last available measurement in the study and
  - a next measurement is available and HCV RNA not detected or HCV RNA < LLOQ detected for this next measurement

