5	3	N	800	50 QOD	75	8 (N=5) 12 (N=14)	Through SVR24 Through EOT	0/5 (0%), SVR24 13/14 (93%), EOT
6	1	Y	800	50 QOD	75	8	Enrolling (N=11)	9/10 (90%), SVR12*
7	1	Y	800	25 QD	75	8	Screening/Planned	N/A
8	1	Y	800	25 QD	75	8	Screening/Planned	N/A
9	1	Y	800	25 QD	75	12	Screening/Planned	N/A
10	1	Y	800	25 QD	75	12	Screening/Planned	N/A
11	2	Y	800	25 QD	75	12	Screening/Planned	N/A
12	2	Y	800	25 QD	75	8	Screening/Planned	N/A
12-15	TBD							

* Subject 11 has completed treatment. SVR visit results pending.

[^] N=10-20 per cohort; In ongoing cohorts in which a dosing regimen is modified (e.g. treatment duration is extended) due to apparently insufficient efficacy/safety, the cohort size may be increased such that 20 subjects at the final dosing regimen are enrolled in that cohort.

This protocol permits enrollment of up to 16 cohorts. The maximum permissible enrollment in this study is up to 320 subjects.

Safety and tolerability will be evaluated on an ongoing basis through assessment of AEs, blood and urine sample analyses, collection of ECG, echocardiograms, vital signs and physical examinations. PK data will be routinely reviewed as it becomes available.

[figure not shown]
All enrolled subjects will be monitored from Day 1 through end of follow up for on treatment failure or relapse as defined by the criteria outlined in Sections 8.2.2–8.2.4. The Sponsor will provide the Investigator with the results of the resistance evaluation to enable them to evaluate the most appropriate therapeutic option for any subject that experiences relapse. Where necessary, the Sponsor will offer appropriate retreatment within a separate protocol or, if the subject is unable or unwilling to participate in that trial, the Sponsor will provide reimbursement for locally available HCV treatment for any subjects that experience on treatment failure or relapse, subject to local regulations. Alternatively, where possible, subjects will be allowed to enroll in a subsequent clinical trial subject to meeting the relevant entry criteria.

PK samples will be obtained at a single time point prior to dosing at all routine study visits while subjects are receiving study medication as well as at Weeks 3 and 6, 2-4 hours postdose, and at Weeks 4 and 8, 6-8 hours postdose. In addition, for a subgroup of up to 250 subjects, additional PK samples will be obtained at Week 2 for all treatment groups.

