4.6.2 Procedures for Subjects Who Discontinue Treatment

Subjects who discontinue from treatment should undergo the Study Completion procedures tabulated in Section 6.1 for the purpose of safety monitoring within 7 days after their last dose of study medication. Any subject that discontinues with ongoing AEs should be followed until resolution of their AE(s) or until the investigator has determined that the AE(s) has stabilized. In addition subjects should be followed up per Table 6-4 off treatment for up to 24 weeks, or when commencing therapy if earlier.

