PK Samples ⁵			X			X	X	X	X
Hematology ⁶		X	X			X	X		X
Serum Chemistries ⁶		X	X			X	X		X
Urinalysis		X	X			X	X		X
ALT/AST ⁶		X	X			X	X	X	X
HCV RNA concentrations ⁷		X	X	X	X	X	X	X	X
Plasma for drug resistance monitoring ⁸			X	X	X	X	X	X	X
Pregnancy Test ⁹		X							X
Optional stored serum sample ¹⁰		X	X			X	X	X	X

⁵ A single predose PK sample will be collected at each indicated visit for AL-335 (and metabolites), ODV and SMV concentrations for all subjects. In addition, PK samples will be collected at Week 3, 2-4 hours postdose, and at Week 4, 6-8 hours postdose. Subjects in the intensive PK subset will have the following samples collected at the Week 2 visit Predose (within 0.5 hour) and 0.5, 1, 2, 3, 4, 6, 9, and 24 hours postdose.

⁶ Blood for routine safety evaluations should be collected in a fasted state.

⁷ Plasma for HCV RNA analysis to be collected predose at Day 1, 2 and 3.

⁸ Plasma collected for HCV RNA resistance monitoring will be collected at the same time as HCV RNA quantification. The Day 1 samples must be collected predose.

⁹ A highly sensitive pregnancy test (e.g., urine or plasma) must be conducted immediately (within 4 days) prior to initiating treatment on Day 1 (local results may be used for this eligibility determination)

¹⁰ For additional safety investigations as needed.

* Weekly visit may occur ± 1 day from the expected visit date.

Table 6-4. Schedule of Events for Post-dosing (Safety and Virology) Follow-up Visits (All Treatment Cohorts)

Post-dosing Follow-up							
Assessment	Early Termination (ET) Visit ¹	Safety Follow-up Visit 4 Weeks (±1 week) After the Last Actual Dose of Study Drug	Virology Follow-up Visits (After end of Treatment ² OR After Time of Treatment Failure [if earlier]) ³				Week 24 (±2 weeks)
			Week 4 (±1 week) ⁴	Week 8 (±1 weeks)	Week 12 (±2 weeks)	Week 18 (±2 weeks)	
Physical Exam ⁵	X	X					
Echocardiogram	X	X					
Vital Signs	X	X					
Triplicate 12 Lead ECG	X	X					
Liver Ultrasound (subjects with cirrhosis)							X
Serum Chemistry w/ ALT & AST	X	X					
Hematology	X	X					
Urinalysis	X	X					
HCV RNA concentration	X	X	X	X	X	X	X
Plasma for drug resistance monitoring	X	X	X	X	X	X	X
AE & Conmed Evaluation	X	X	X	X	X	X	X
PK Samples ⁶	X	X	X	X	X	X	X

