**Otherwise SVR12 is classified as a failure (0).**

\* Confirmed means that the criterion should be fulfilled at 2 or more consecutive time points or at the last observed time point.

Time point of SVR12:

- 12 weeks after the actual EOT (i.e. the last available measurement in the SVR12 analysis window)
- or, if not available, the first available measurement at least 12 weeks after the actual EOT (i.e. the first available measurement after the SVR12 analysis window)
- or, if not available (i.e. no measurement at least 12 weeks after the actual EOT), the subject is considered a failure.

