#### 9.3.1 Definitions

**SVR4, SVR18 and SVR24** are defined similarly as SVR12 but with 4 weeks, 18 weeks and 24 weeks respectively, instead of 12 weeks.

In addition, for SVR24, the time point of SVR is defined as follows:

- 24 weeks after actual EOT (i.e. the last available measurement in follow up Week 24 analysis window)
- or, if not available, the first measurement available, after the follow-up Week 24 analysis window
- or, if not available, the last measurement available in the SVR18 analysis window, on condition that the time point of SVR24 has been reached

- or, if not available, the last measurement available in the follow up Week 12 analysis window (on condition that the time point of SVR24 has been reached)
- or, if not available, the subject is considered as not having SVR24

For SVR18, the timepoint of SVR is defined as follows:

- 18 weeks after the actual EOT (i.e. the last available measurement in follow up Week 18 analysis window)
- or, if not available, the subject is considered as not having SVR18

**On-Treatment failure** is defined as subjects who did not achieve SVR12 and with confirmed HCV RNA  $\geq$ LLOQ at the actual end of study drug treatment. Includes subjects:

- With viral breakthrough, defined as a confirmed increase of  $>1$  log10 in HCV RNA from nadir, or confirmed HCV RNA of  $>100$  IU/mL in subjects whose HCV RNA had previously been  $<$ LLOQ while on treatment.
- With inadequate virologic response, defined as  $<1$  log10 decline from baseline in HCV RNA after 4 weeks of treatment
- Who do not experience viral breakthrough or inadequate virologic response and have confirmed HCV RNA  $\geq$ LLOQ at the actual end of study drug treatment (e.g., completed study drug treatment, discontinued due to adverse events, withdrawal of consent).

**Viral Relapse** is defined as follows:

Subjects who achieved HCV RNA  $<$ LLOQ at the actual end of study drug treatment and developed HCV RNA  $\geq$ LLOQ during post-treatment follow up.

**Failure (No SVR12):** Subjects who did not achieve SVR12, including:

- On-treatment failure (see above)
- Post-treatment failure, including subjects with:
  - Viral relapse (see above)
  - Missing HCV RNA at time point of SVR12

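### The SVR rules in SAP 9.2.1 and 9.3.1 do not look back for a confirmed relapse or for non-study HCV therapy, so a treatment completer who relapses and takes local therapy can be scored as an SVR success

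*SAP*

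**What the plan says.** SAP 9.2 names SVR12 as the primary efficacy endpoint, and 9.2.1 classifies it by an "algorithm based on HCV RNA values 12 weeks after the actual end of treatment". An undetected result at the time point is a success with no further condition. A result below LLOQ but detected is a success if it is a confirmation sample, the last sample, or followed by another value below LLOQ. Even a result at or above LLOQ can be a success, provided that the sample is neither confirmatory nor the last and "a next measurement is available and HCV RNA not detected or HCV RNA < LLOQ detected for this next measurement". The sample used is the last one in the SVR12 window, or failing that the first one after it. With no sample at or beyond Week 12, the subject is a failure. SAP 9.3.1 adds that SVR4, SVR18 and SVR24 "are defined similarly as SVR12 but with 4 weeks, 18 weeks and 24 weeks respectively, instead of 12 weeks".

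On retreatment, protocol 2.1 offers a separate retreatment protocol. If the subject cannot or will not join it, "the Sponsor will provide reimbursement for locally available HCV treatment for any subjects that experience on treatment failure or relapse". Table 6-4, footnote 4, mentions relapsers when it describes the Week 4 virology visit, so they remain in virology follow-up.

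Two rules limit what is collected afterwards. Under protocol 4.6.2, subjects who discontinue study drug are followed for up to 24 weeks "or when commencing therapy if earlier". Under 4.6.3, a subject who enters a clinical study of an investigational drug must first withdraw from this one.

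**The concern.** Protocol 8.2 describes SVR as HCV RNA kept below LLOQ after treatment ends. The SAP algorithm tests something narrower: the value at one time point, sometimes with the next one. It never asks whether the subject had already relapsed or whether a later suppressed value was obtained on another regimen.

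A relapser who completed study drug and then takes local therapy is covered by neither 4.6.2 nor 4.6.3. No passage makes that subject wait until follow-up ends. The effect of the other regimen would then be credited to the study regimen. The error can only raise SVR, and it would be largest in the cohorts with most relapse. Protocol 10.8 plans to pool these efficacy data with another study to support a Phase 3 trial.

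**Working it through.** **1. Windows.** SAP 3.2 starts the follow-up phase on the day after last dose + 3 days, so follow-up day d is d + 3 days after last dose. The Week 12 window, days 68–102, is therefore days 71–105 after last dose. Week 18 (103–144) becomes 106–147, and Week 24 (145 onward) becomes 148 onward.

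**2. Is there time to retreat?** Suppose relapse is seen at follow-up Week 4 (day 28). Protocol 6.2.3 asks for a retest preferably within 2 weeks (about day 42). No passage gives a start date for retreatment; day 56 is an assumption. Samples at Weeks 12, 18 and 24 (days 84, 126, 168) would then fall 84 − 56 = 28, 126 − 56 = 70 and 168 − 56 = 112 days into the new therapy. A later start would spare SVR12 but could still affect SVR18 or SVR24, which is why those two are more exposed.

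**3. The SAP rule applied to four hypothetical histories.**

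| History | SVR4 | SVR12 | SVR18 | SVR24 |
|---|---|---|---|---|
| A. Confirmed relapse at Week 4, local therapy from about day 56, undetected at Weeks 12, 18, 24 | failure | success | success | success |
| B. First value ≥LLOQ at Week 12, no retest, retreated, undetected at Weeks 18 and 24 | success | success | success | success |
| B2. As B, with a confirming retest inside the Week 12 window | success | failure | success | success |
| C. Confirmed relapse at Week 4, then withdrawal to enter another study | failure | failure | failure | failure |

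A succeeds because an undetected value needs no further condition. B succeeds at SVR12 through the next-measurement clause, though it requires the retest in protocol 6.2.3 to have been missed. C shows that withdrawal closes the gap.

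**4. Classification of history A under the SAP.** SAP 9.3.1 defines viral relapse as HCV RNA below LLOQ at actual end of treatment followed by a value at or above LLOQ in follow-up, with no condition on SVR12. Subject A meets it and is also an SVR12 success. The SAP lists relapse as a form of failure, but only among subjects who did not achieve SVR12, so that list does not override the algorithm. The ordering of failure types in 9.3.2 likewise applies only to subjects already scored as failures.

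**5. Size.** The planned interval is the two-sided Clopper-Pearson 95% CI: lower limit the 2.5% quantile of Beta(x, n − x + 1), upper limit the 97.5% quantile of Beta(x + 1, n − x), with upper limit 100% when x = n. This reproduces protocol 9.3: 18/20 gives 68.3–98.8% and 19/20 gives 75.1–99.9%.

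One subject moves SVR by 1/20 = 5 points in a cohort of 20 and 1/10 = 10 points in a cohort of 10.

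SAP section 4 pools Cohort 1b with the 8-week part of Cohort 4. Protocol Table 1-1 reports 18/20 and 3/5 at SVR24, so 21/25 pooled. Protocol 1.2.1.2 reports 2 relapses in each cohort; I take the two in Cohort 4 to be the two non-responders of its 8-week part. With k of these four scored as successes:

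| k | SVR | 95% CI |
|---|---|---|
| 0 | 21/25 = 84.0% | 63.9–95.5 |
| 1 | 22/25 = 88.0% | 68.8–97.5 |
| 2 | 23/25 = 92.0% | 74.0–99.0 |
| 3 | 24/25 = 96.0% | 79.6–99.9 |
| 4 | 25/25 = 100% | 86.3–100 |

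The last row requires all four to have been retreated locally, to have stayed in follow-up and to have been suppressed at the time point.

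**The case against.** The strongest reply is that few subjects are exposed. The separate retreatment protocol comes first and local therapy is the alternative. Entering an investigational-drug study forces withdrawal, which leaves no later sample and so a failure. Viral breakthrough and inadequate response require permanent discontinuation (4.6.1), after which 4.6.2 ends follow-up when therapy starts. This stands. What remains is essentially the completer who relapses and takes local therapy.

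Timing is the second reply. Protocol 1.7 puts sequencing before the choice of retreatment. Section 1.2.1.2 reports that sequencing of the Cohort 4 relapsers was not yet available, although the 8-week part had already passed SVR24. This makes the SVR12 route possible rather than shown to be likely. It weakens the case less for SVR18 and SVR24.

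Several stronger readings are tempting but not supported:

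- *The subject disappears from the relapse count.* The protocol's Definitions table makes relapse conditional on not achieving SVR12, but SAP 9.3.1 and protocol 8.2.3 do not. In the planned analysis the subject is still counted as a relapse.
- *Table 6-4 times a relapser's visits from the relapse.* The heading "After Time of Treatment Failure [if earlier" carries footnote 3, which points to on-treatment failure. Footnote 4 is the text that shows relapsers in follow-up.
- *Cohort 5 at 8 weeks could go from 0/5 to 5/5.* No passage says that those five failures were relapses.
- *Inadequate regimens would go undetected.* Futility (protocol 4.8.1) uses relapse at any follow-up visit, not the SVR algorithm.

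Listings of HCV RNA and concomitant medication, and individual viral-load plots, would let a careful reader find such a subject. They would not correct the tabulated rate.

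**Conclusion.** The defect is real but narrow. As written, the SAP can score a treatment completer who relapsed and took local HCV therapy as a success at SVR12, and more readily at SVR18 and SVR24. The same subject would be a viral relapse under the SAP's own definition, which is a contradiction.

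The size is 5 points per subject in a cohort of 20. For the pooled 8-week group without simeprevir, the range runs from 84.0% to a hypothetical 100%. That range rests on an assumed number of retreated and suppressed relapsers, between 0 and 4.

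A reader might infer that reported results are already inflated. The documents do not show this: Table 1-1 counts 18/20 and 3/5 at SVR24, so the documented relapsers still appear as non-responders. The protocol does not say which rule produced those counts, so they do not show that the SAP rule is safe either.

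This should be fixed before database lock. It does not undermine the trial, whose primary endpoint is safety and which tests no hypothesis; SVR is secondary in the protocol.

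**What to change.** Add two rules to SAP 9.2.1 and 9.3.1:

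1. HCV RNA values on or after the first dose of any non-study anti-HCV therapy are not used for any SVR classification, either as the time-point value or as the next measurement. The subject is a failure at every SVR time point after that date, and the SVR24 fallback to earlier windows does not apply.
2. A subject with HCV RNA below LLOQ at actual end of treatment and confirmed HCV RNA at or above LLOQ in follow-up, who then starts such therapy, is counted as viral relapse and as SVR failure at all later time points.

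Under these rules histories A, B and B2 become failures at SVR12, SVR18 and SVR24, and C is unchanged. Start dates come from the concomitant-medication data, which Table 6-4 collects at every follow-up visit and protocol 8.1.3 records through study completion.

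Protocol 2.1, 4.6.2, 4.6.3 and Table 6-4 should also be reconciled on what follow-up data are collected once other HCV therapy has begun. The relapse definition in the protocol's Definitions table should be aligned with the one in the SAP.

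The cost is two sentences and one programming flag, with no new data collection. The downside is that some SVR rates may be slightly lower than the current rule would give.

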**Otherwise SVR12 is classified as a failure (0).**

\* Confirmed means that the criterion should be fulfilled at 2 or more consecutive time points or at the last observed time point.

Time point of SVR12:

- 12 weeks after the actual EOT (i.e. the last available measurement in the SVR12 analysis window)
- or, if not available, the first available measurement at least 12 weeks after the actual EOT (i.e. the first available measurement after the SVR12 analysis window)
- or, if not available (i.e. no measurement at least 12 weeks after the actual EOT), the subject is considered a failure.

### 9.2.2 Analysis Methods

The number and proportion of subjects with SVR12 will be tabulated overall and by cohort, a two-sided Clopper-Pearson 95% CI will be constructed.

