10.7 Efficacy Analysis

Efficacy will be determined by assessing HCV RNA results by time. Where appropriate, data will be pooled if identical regimens and patient populations are evaluated in multiple cohorts. Efficacy data will be summarized in tables and by subject listings, describing percent (un)detectable. Descriptive statistics will be utilized to summarize efficacy analyses.

Viral sequencing will also be analyzed to look for evidence of emergence of resistance. Pre-treatment polymorphisms in the HCV NS3/4A, NS5A and NS5B regions, as applicable, in all subjects and relevant changes in the HCV NS3/4A, NS5A and NS5B regions, as applicable, in subjects not achieving SVR will be tabulated and described. The effect of pre-treatment NS3/4A, NS5A and NS5B polymorphisms, as applicable, on treatment outcome will be explored. These changes in viral sequence will not be regarded as AEs or SAEs. Additional exploratory characterization of the viral sequence and phenotype may be performed and will be reported accordingly.

Please refer to the statistical analysis plan for more details.

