#### 4. Statistical considerations

Efficacy and safety data will be analysed using SAS® software version 9.4 (SAS institute Inc. ██████ USA).

Pharmacokinetic data from the PK substudy will be analysed using Phoenix® WinNonLin® version 6.4 (Pharsight) and SAS® software version 9.4 (SAS Institute Inc. ██████ USA) for final analysis.

Descriptive statistics will be supplied according to the nature of the criteria:

- Quantitative variable: sample size, arithmetic mean, standard deviation (SD), standard error of the mean (SEM), minimum, median and maximum, and quartiles if necessary (with geometric mean, arithmetic and geometric coefficients of variation (CV), and quartiles for PK parameters, geometric mean will not be reported in case of value equal to 0).
- Qualitative variable: sample size, absolute and relative frequencies per class. Percentages will be provided with one decimal place.

Safety data will be organized by cohort.

All safety and pharmacokinetics listings will be sorted by cohort, subject, and measurement time if applicable.

For all except pharmacokinetics data, cohorts that evaluate the same treatment regimen for the same duration (e.g., Cohort 1b and the first 5 subjects in Cohort 4) will be pooled (using Label “Cohort 1b+Cohort 4 (8 Weeks).” If multiple treatment durations and/or regimens were assessed in a single cohort, the data for that cohort will be presented separately (e.g. Cohort 4 (12 weeks) will be separate from Cohort 4 (8 weeks), which will be pooled with cohort 1b). For cohorts with different clinical characteristics (e.g. HCV genotype, cirrhosis status),

treatment regimens or same treatment regimen but with different durations, data will be presented separately.

For pharmacokinetic data, cohorts that evaluate the same treatment regimen (including study medications and doses) in the same population (cirrhotic vs non-cirrhotic), whatever the duration, or HCV genotype will be pooled, i.e. the presentation of cohorts will be:

- Cohort 1,
- Cohort 1b+4,
- Cohort 2+Cohort 3+Cohort 5,
- Cohort 6.
- Cohort 7+Cohort 8+Cohort 9+Cohort 10+Cohort 11+Cohort 12

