**Type I error rate**

No significance testing will be performed. However, two-sided Clopper-Pearson 95% CI will be constructed around the proportion of subjects with sustained virologic response (SVRx) and other virologic response parameters, for each cohort.

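### SAP 9.2.2 tabulates an overall SVR12 across unlike cohorts, possibly with a confidence interval, against the SAP's own rule for keeping such cohorts apart

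*SAP*

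**What the plan says.** SAP 9.2 names SVR12 as the primary efficacy endpoint, although in the protocol safety is primary and SVR secondary. SAP 9.2.2 gives the analysis in one sentence: "The number and proportion of subjects with SVR12 will be tabulated overall and by cohort, a two-sided Clopper-Pearson 95% CI will be constructed". SAP 9.3.2 applies the same analysis to SVR4 and SVR24.

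Other places bear on whether such a total should exist and what should accompany it:

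- SAP 4 sets the grouping rule for all data except pharmacokinetics. Cohorts given the same regimen for the same duration are pooled. For cohorts that differ in clinical characteristics (genotype and cirrhosis status are its examples), the rule continues: "treatment regimens or same treatment regimen but with different durations, data will be presented separately".
- Protocol 10.7, on efficacy: "Where appropriate, data will be pooled if identical regimens and patient populations are evaluated in multiple cohorts".
- SAP 4, under the type I error heading, places the Clopper-Pearson interval around "the proportion of subjects with sustained virologic response (SVRx) and other virologic response parameters, for each cohort". SAP 9.1.1 repeats this: "constructed around the proportion of subjects with SVRx and other virologic response parameters, for each cohort".
- SAP 9.1.1 also states: "No significance testing will be performed".
- The group table in SAP 3.1 gives the combined groups for presenting non-PK data. It puts Cohorts 6, 7 and 8 in one group, Cohorts 1b and 4 in one group, and all of Cohort 5 in one group.

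**The concern.** The cohorts in SAP 3.1 cover three genotypes, cirrhosis and no cirrhosis, regimens with and without simeprevir, two AL-335 doses, two odalasvir dose levels on different schedules, and durations of 6, 8 and 12 weeks. No patient population or treatment corresponds to their sum, so an overall SVR12 has no defined target. A programmer also cannot follow both SAP 9.2.2 and SAP 4 as written.

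The weights in such a total are the cohort sizes, and these respond to results. Protocol 1.2.1.2 reports that Cohort 4 was stopped at 13 subjects after relapses. It also reports that Cohort 5 was moved from 8 to 12 weeks on early antiviral data, which left 5 subjects at 8 weeks. Protocol 4.8.1 allows enrolment in an arm to be halted for futility. Protocol 2.1 sets cohorts at 10 to 20 subjects and lets a modified cohort grow to 20 at its final regimen. Protocol 4.7 lets the sponsor omit any of Cohorts 7 to 15. A regimen that performs badly will therefore tend to get less weight. At stake is a single figure for the SAP's named primary efficacy endpoint that can shift with the cohort mix while no regimen's effect changes.

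**Working it through.** **Inputs.** SVR counts are from Protocol Table 2-1 (data as of 17 February 2017). SVR24 is used where that is the figure shown, and SVR12 for Cohort 4 at 12 weeks and Cohort 6. The 14 Cohort 5 subjects at 12 weeks are left out because only end-of-treatment data are given. One of the 11 Cohort 6 subjects has a result pending.

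**Formula.** For x successes in n, the Clopper-Pearson 95% limits are the 0.025 quantile of Beta(x, n − x + 1) and the 0.975 quantile of Beta(x + 1, n − x). The lower limit is 0 if x = 0, and the upper limit is 1 if x = n.

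**The plan's own figures.** Protocol 9.3 gives 68.3% to 98.8% for 90% of 20 subjects and 75.1% to 99.9% for 95% of 20. The formula returns the same limits for 18/20 and 19/20. The protocol states no precision for an overall SVR12.

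**Results by the SAP 4 rule.**

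| Group | SVR | 95% CI |
|---|---|---|
| Cohort 1 | 20/20 = 100% | 83.2–100 |
| Cohorts 1b + 4 (8 weeks) | 21/25 = 84.0% | 63.9–95.5 |
| Cohort 2 | 20/20 = 100% | 83.2–100 |
| Cohort 3 | 20/20 = 100% | 83.2–100 |
| Cohort 4 (12 weeks) | 7/8 = 87.5% | 47.3–99.7 |
| Cohort 5 (8 weeks, GT3) | 0/5 = 0% | 0–52.2 |
| Cohort 6 (cirrhosis) | 9/10 = 90.0% | 55.5–99.7 |

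**The overall figure.** Successes: 20 + 21 + 20 + 20 + 7 + 0 + 9 = 97. Subjects: 20 + 25 + 20 + 20 + 8 + 5 + 10 = 108. So 97/108 = 89.8% (82.5–94.8).

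**Common success probability.** An interval on that total assumes a single rate. Across the eight cohort-by-duration rows (1b and the 8-week part of Cohort 4 taken separately), the heterogeneity chi-square is 55.8 on 7 degrees of freedom. Some expected counts are small, so a permutation reference was used, giving p < 0.001.

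**Dependence on cohort size.** Hold every other group as observed, keep the GT3 8-week rate at 0%, and change only its size n. The overall rate is then 97/(103 + n):

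- n = 0: 97/103 = 94.2% (87.8–97.8)
- n = 5, as observed: 97/108 = 89.8% (82.5–94.8)
- n = 10: 97/113 = 85.8% (78.0–91.7)
- n = 20: 97/123 = 78.9% (70.6–85.7)

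The swing is 94.2 − 78.9 = 15.3 points, and the intervals at the two ends do not overlap.

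**Sensitivity to the omitted group.** Adding the 14 Cohort 5 subjects at 12 weeks gives 97/122 = 79.5% if none succeeds and 111/122 = 91.0% if all do.

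**The SAP 3.1 group table.** Cohort 6 receives odalasvir 50 mg QOD, and Cohorts 7 and 8 receive 25 mg QD, yet they share a group. Cohorts 1b and 4 share a label across 8 and 12 weeks, although SAP 4 uses Cohort 4 as its example of a split. A single Cohort 5 row would merge 0/5 at 8 weeks with the 12-week subjects. If all 14 of those succeeded it would read 14/19 = 73.7%, a rate that belongs to neither duration.

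**The case against.** The strongest reply is that this is an ordinary total column. The SAP uses an overall column routinely for disposition, deviations, demographics and medications (5.2, 5.3, 6.1, 6.2, 6.4), and SAP 4 can be read as governing how cohorts are grouped and labelled. Protocol 10.7 opens with a qualifier and states when pooling is done. It does not say that nothing else may be summed. Since SAP 4 and 9.1.1 both scope the interval to each cohort, 9.2.2 may intend a count and percentage overall with intervals by cohort. These points stand as limits. An interval on the overall row is a possible reading, not a certain one, and the conflict with Protocol 10.7 is with its stated pooling condition, not with an express prohibition.

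The illustration has limits too. The 97/108 is not the final overall SVR12: it mixes SVR12 with SVR24, omits 15 subjects (14 in Cohort 5, 1 in Cohort 6) and predates Cohorts 7 to 12. Twenty GT3 subjects completing 8 weeks at 0% is an end point of the range that the plan worked against, because the duration was extended on early data.

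A reader might infer that an overall interval would be falsely narrow. The figures do not show this. The binomial standard error is √(0.898 × 0.102/108) = 2.9 points, against 2.0 points if the cohort mix is treated as fixed, so the interval is if anything too wide. The 2.0 is itself a poor benchmark, because it assigns zero variance to the 65 subjects in groups with 0% or 100% response.

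**Conclusion.** The point holds as an internal inconsistency with a misleading descriptive summary as its consequence. SAP 9.2.2, and through 9.3.2 the SVR4 and SVR24 analyses, ask for a total that conflicts with SAP 4 and with the pooling condition in Protocol 10.7, and the scope of the interval is unclear. On the data in Table 2-1 the total is about 90%, over group rates from 0% to 100%. It can move by about 15 points through the size of one group alone. That size rests on the observed counts, on mixing SVR12 and SVR24, and on holding the GT3 8-week rate at 0%.

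Three stronger readings are not supported:

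- **That failing regimens would be hidden.** The same sentence in 9.2.2 requires by-cohort results, and virologic failures are tabulated and listed. This protection does depend on the by-cohort rows following SAP 4 and not the SAP 3.1 table.
- **That an error rate or a decision is affected.** Nothing is tested, and futility is judged by cohort or regimen (Protocol 4.8.1). The pooling to support Phase 3 has its own analysis plan (Protocol 10.8).
- **That the sponsor alone can set the figure.** Changes to cohort parameters also need the Principal Investigator's agreement (Protocol 2.1).

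**What to change.** 1. In SAP 9.2.2, delete *overall*, which also removes it from SVR4 and SVR24 through 9.3.2. Alternatively, keep the total as a count with no interval.
2. State in 9.2.2, in agreement with SAP 4 and 9.1.1, that Clopper-Pearson intervals are given only for groups defined by the SAP 4 rule.
3. Align the group table in SAP 3.1 with that rule: Cohort 6 (odalasvir 50 mg QOD) separate from Cohorts 7 + 8 (25 mg QD); the 8-week part of Cohort 4 pooled with 1b and its 12-week part separate; the 8-week and 12-week parts of Cohort 5 separate.

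The cost is an edit to one sentence and a few table cells, and the loss of a single total row. Every result that corresponds to a regimen and population is kept.
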